## 15 Appendices

### APPENDIX 1 – ECOG PERFORMANCE STATUS

ECOG*	STATUS
0	Fully active, able to carry on all pre-disease performance without restriction
1	Restricted in physically strenuous activity but ambulatory and able to carry out work of a light or sedentary nature, e.g., light house work, office work
2	Ambulatory and capable of all self-care but unable to carry out any work activities. Up and about more than 50% of waking hours
3	Capable of only limited self-care, confined to bed or chair more than 50% of waking hours
4	Completely disabled. Cannot carry on any self-care. Totally confined to bed or chair
5	Dead

\* As published in American Journal of Clinical Oncology [9]

**APPENDIX 2 – PET-CT RESPONSE DEFINITIONS FOR CLINICAL TRIALS\***

RESPONSE	DEFINITION	NODAL MASSES
CR	Disappearance of all evidence of disease	a. FDG-avid or PET positive prior to therapy; mass of any size permitted if PET negative b. Variably FDG-avid or PET negative; regression to normal size on CT
PR	Regression of measurable disease and no new sites	>50% decrease in SPD of up to 6 largest dominant masses; no increase in size of other nodes a. FDG-avid or PET positive prior to therapy; one or more PET positive at previously involved site b. Variably FDG-avid or PET negative; regression on CT
SD	Failure to attain CR/PR or PD	a. FDG-avid or PET positive prior to therapy; PET positive at prior sites of disease and no new sites on CT or PET b. Variably FDG-avid or PET negative; no change in size of previous lesions on CT
RELAPSED DISEASE OR PD	Any new lesion or increase by >50% of previously involved sites from nadir	Appearance of a new lesion(s) >1.5 cm in any axis, >50% increase in SPD of more than one node, or >50% increase in longest diameter of a previously identified node >1cm in short axis Lesions PET positive if FDG-avid lymphoma or PET positive prior to therapy

Abbreviations: CR, complete remission; FDG, [F] fluorodeoxyglucose; PET, positron emission tomography; CT, computed tomography; PR, partial remission; SPD, sum of produce of the diameters; SD, stable disease; PD, progressive disease.
		

\*As published in Journal of Clinical Oncology [6]

## **APPENDIX 3 – DEFINITION OF RESPONSE CRITERIA**

Conventional CT response to chemotherapy will be defined as follows:

### **COMPLETE RESPONSE (CR)**

Normal tumour markers, no clinical or radiological evidence of disease or surgery indicating no viable cancer cells in resected specimens (if surgery is done at this stage).

### **PARTIAL RESPONSE (PR) (marker positive)**

More than 90% reduction in tumour markers and/or >50% reduction in tumour masses determined by radiology for at least 28 days following cessation of chemotherapy without normalisation of tumour markers.

### **PARTIAL RESPONSE (PR) (marker negative)**

Normalisation of markers and residual mass (marker negative PR) for at least 28 days

### **STABLE DISEASE**

Less than 50% reduction in tumour markers for at least 1 month following chemotherapy.

### **PROGRESSIVE DISEASE**

Less than 50% reduction in tumour markers or progression within 28 days of stopping chemotherapy

## **APPENDIX 4 – DEAUVILLE CRITERIA**

Deauville criteria:-

Visual interpretation of the PET-CT scan uses a 5-point scale.

Baseline and PET-CT scans are scored according to uptake in sites initially involved by metastatic seminoma: (1) no uptake, (2) uptake = mediastinum blood pool, (3) uptake = liver, (4) moderately increased uptake > liver, or (5) markedly increased uptake > liver and/or new lesions. A score of 1-3 is regarded as negative and 4 or 5 as positive.

### **Deauville Criteria**

- **Score 1 no uptake**
- **Score 2 uptake  $\leq$  mediastinum**
- **Score 3 uptake  $>$  mediastinum but  $\leq$  liver**
- **Score 4 uptake  $>$  liver at any site**
- **Score 5 uptake  $>$  liver and new sites of disease**

Moskowitz C H Hematology 2012;2012:397-401

©2012 by American Society of Hematology

\*As published in ASH Education [10]

**The report will be emailed as pdf to the nhs.net email address specified above**

CAR-PET PET-CT Scan Review Request Form\_Mount Vernon Hospital\_v2.0 dated 05AUG2014.PDF

## APPENDIX 7 – SUBMISSION OF IMAGES FOR CENTRAL REVIEW AND ESCALATION PROCESS

## **APPENDIX 8 –IMAGING PROTOCOL**

### **Scanning Protocol**

1. Administer 350-400MBq 18FDG.
2. The emission scan should start 60 minutes after tracer injection from the skull base to the upper thigh.
3. A low dose CT should be performed for attenuation correction and anatomical localisation from the skull base to the upper thigh.

Acquisition should be performed using the institution's standard protocol with regard to time per bed position, 2D or 3D, CTAC-parameters, reconstruction parameters and algorithms etc. Both attenuation corrected and non-attenuation corrected data sets should be reconstructed.

### **Radiation Dosimetry**

The effective radiation dose associated with an administration of 400 MBq 18-FDG is 10.0mSv (ARSAC Notes for Guidance 1998). The CT attenuation correction using 80mA and 150KV will be approximately 8 mSv for scan suggested

### **Image Data Transfer**

Image data must be transferred to UCLH Central Review ([name]) via the secure NHS IEP.

The following file is required:

- Attenuation corrected PET data acquired from the base of the skull to the upper thigh
- Non attenuation corrected PET data acquired from the base of the skull to the upper thigh
- Low dose CT data acquired from the base of the skull to the upper thigh
- CT scout views are not required

All files must be clearly marked with the pre-arranged filename. The patient's full name can be used when using the secure IEP system. **The trials office cannot have any correspondence sent to them via email or post with patient personal identifiers being present, only initials, date of birth and trial numbers are applicable.**

*This page to be left blank.*

K-M	Kaplan-Meier
MedDRA	Medical dictionary for regulatory activities
NCI	National cancer institute
PET	Positron emission tomography
PFS	Progression-free survival
PID	Percentage intended dose
PR	Partial response
RDI	Relative dose intensity
SAE	Serious adverse event
SS	Safety set

1 Introduction

1.1 Preface

Metastatic seminoma is a relatively infrequent disease entity. The conventional treatment for it, namely cisplatin and etoposide with or without bleomycin, has a progression-free survival (PFS) rate at 3 years of over 81% compared to 71% treated with carboplatin area under the curve (AUC) 7 [1]. Several studies have addressed the use of single agent carboplatin in metastatic seminoma. Studies have generally concluded that although PFS is inferior to that seen with cisplatin based therapy, as a large number of relapsing patients could be salvaged, the overall survival was unchanged and indeed toxicity was substantially reduced [1, 2].

The Orchid Clinical Trials Group recently completed a study in metastatic seminoma using carboplatin AUC-10. Twenty patients received this dose of carboplatin for metastatic seminoma, with a median follow up of 29.4 months. Following the closure of the study a further 20 patients have received carboplatin AUC-10. In total 40 patients have been treated. There have been 2 relapses to date (5%), compared to the 18% relapse seen within the first 2 years of treatment of 28 patients who received AUC 7 or less with a median follow up of 135 months. The relapsed patients were successfully salvaged using conventional chemotherapy. As nearly all relapses occur within 2 years of therapy, a 2 year PFS is an appropriate endpoint for this phase II study.

In this most recent study, the protocol stipulated that all patients who were not in complete remission by day 21 of the first cycle would receive 4 rather than 3 cycles. This led to all those who essentially had greater than 2B disease requiring 4 cycles. This was probably unnecessary as most patients achieved a complete response (CR) eventually – it just took time for the masses to shrink.

It is hoped, in the Car-PET study, that by substituting conventional computed tomography (CT) for positron emission tomography (PET) CT a greater proportion of patients will achieve a complete metabolic response and therefore the 4th cycle may be avoided in more patients. This will allow shortening of the treatment and reduction in the use of blood products as most of the blood transfusions required occur during the 4th cycle of carboplatin.

1.2 Purpose of the Analyses

These analyses will assess the safety, efficacy and toxicity of carboplatin AUC-10 in metastatic seminoma in a multi-centre setting. The aim is to see if, by using Fluorodeoxyglucose (FDG) PET-CT to assess metabolic response, the number of patients requiring 4 cycles can be reduced.

2 Study Objectives and Endpoints

Primary Objective	Endpoints
2-year PFS rate	PFS rate for carboplatin AUC-10 at 2 years measured from the date of study enrolment to the date of disease progression or death. The study result will be considered positive if the PFS rate for patients on carboplatin AUC-10 is consistent with a true difference of 15% or more from standard chemo i.e. if there are at least 39 PFS patients out of the first 45 patients at 2 years.
Secondary Objectives	Endpoints

Metabolic response rate	Proportion of patients meeting each of the response categories as defined in Appendix 2 of the protocol.
Overall response	Overall response at the end of the treatment
Overall survival	Median overall survival time measured from the date of study enrolment to the date of death.
Toxicity level	Percentage of adverse events (grade 3 or 4 according to CTCAE version 4.03 criteria) in terms of treatment cycle of any type (including vomiting, nausea and diarrhoea).

3 Study Methods

[figure not shown]
3.1 General Study Design and Plan

This is a single arm phase II study to assess the safety, efficacy and toxicity of carboplatin AUC-10 in metastatic seminoma. Up to 50 patients will be recruited into the study over four years (assuming 5 patients may drop out for reasons other than disease progression/intolerable side effects). 45 evaluable patients will be necessary to establish activity of carboplatin AUC10 in this setting. Patients will be recruited for 48 months. Patients will be followed up as part of the study for 2 years following completion of treatment. The end of the study will be 3 months after the date when the last patient has completed his final follow up visit.

Prior to the commencement of treatment, the patient should have a baseline PET-CT scan and a contrast enhanced CT scan performed within 28 days of study entry. Patients will be treated with carboplatin AUC-10 every 3 weeks (3 weeks=1 cycle) and on day 17-21 of the first cycle a repeat PET-CT scan will be performed. If the patient has a complete metabolic response (see Appendix 3 of the protocol), a further 2 cycles of carboplatin will be given, leading to a total of 3, and if the patient has not had a complete metabolic response but is responding, a further 3 cycles of carboplatin will be given.

If a patient is showing no response to treatment then the patient will be taken off study and will receive conventional therapy using a cisplatin-based combination.

Figure 1: Treatment Flowchart

3.2 Inclusion-Exclusion Criteria and General Study Population

3.2.1 Inclusion Criteria

Each patient must meet all of the following inclusion criteria to be enrolled in the study:

1. Metastatic seminoma – International Germ Cell Cancer Collaborative Group (IGCCCG) good prognosis.
2. Glomerular filtration rate of over 25 ml/min (creatinine clearance should preferably be assessed using an ethylenediaminetetraacetic acid [EDTA] clearance).
3. Eastern cooperative oncology group (ECOG) performance status 0-3.
4. Normal Alpha-fetoprotein (All levels of Human chorionic gonadotropin and lactate dehydrogenase are acceptable).
5. Males aged greater than 18 and less than 75 years.
6. Able to give written informed consent prior to study entry.
7. Patients must be sterile or agree to use adequate contraception during the period of therapy.

3.2.2 Exclusion Criteria

Patients meeting any of the following exclusion criteria are not to be enrolled in the study:

1. Metastatic seminoma with any non-pulmonary visceral metastases.
2. Raised Alpha-fetoprotein.
3. Any previous chemotherapy or radiotherapy.
4. Currently enrolled in any other investigational drug study.
5. Other malignancy except basal cell.

3.3 Randomisation and Blinding

This is an open-label single arm phase II study therefore randomisation and blinding are not applicable.

3.4 Study Variables

3.4.1 Primary and Secondary Variables

3.4.1.1 Primary Efficacy Variables

3.4.1.1.1 Progression-Free Survival (PFS)

PFS is defined as the time between the date of enrolment to first evidence of disease progression based on central review or death, whichever occurs first. For patients who have not died or experienced disease progression at the end of study, PFS will be censored on the last date the patient was known to be progression-free. Patients with no post-baseline tumour assessment will be censored at the date of enrolment plus 1 day. The PFS time will always be derived based on scan/assessment dates not visit dates.

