### **1.3 Clinical data to date**

The Orchid Clinical Trials Group recently completed a study in metastatic seminoma using carboplatin AUC-10. Twenty patients received this dose of carboplatin for metastatic seminoma, with a median follow up of 29.4 months. Following the closure of the study a further 20 patients have received carboplatin AUC-10. In total 40 patients have been treated. There have been 2 relapses to date (5%), compared to the 18% relapse seen within the first 2 years of treatment of 28 patients who received AUC 7 or less with a median follow up of 135 months.

The relapsed patients were successfully salvaged using conventional chemotherapy. As nearly all relapses occur within 2 years of therapy, a 2 year progression-free survival is an appropriate endpoint for this phase II study.

In this most recent study, the protocol stipulated that all patients who were not in complete remission by day 21 of the first cycle would receive 4 rather than 3 cycles. This led to all those who essentially had greater than 2B disease requiring 4 cycles. This was probably unnecessary as most patients achieved a CR eventually – it just took time for the masses to shrink.

It is hoped that by substituting conventional CT for PET CT a greater proportion of patients will achieve a complete metabolic response and therefore the 4th cycle may be avoided in more patients. This will allow shortening of the treatment and reduction in the use of blood products as most of the blood transfusions required occur during the 4th cycle of carboplatin.

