### 5.3.3 Central review of PET-CT scans

There are currently no well validated metabolic response criteria for PET-CT in seminoma. Hence, we will use the criteria for assessment of response developed for the evaluation of lymphoma [6].

A Complete Response will be defined as **complete resolution** of all previously seen sites of nodal and metastatic disease. If residual sites of metastatic disease persist then the PET-CT will be used to evaluate metabolic activity.

Metabolic Complete Remission will be defined as the level of FDG uptake within the lesion that is no greater than normal mediastinal uptake these patients will receive 3 cycles in total. Lesions with uptake greater than the mediastinum will be viewed as non-complete

responders. The PET data will be viewed on standardised SUV (standardised uptake value) setting of between 0 and 5.0 and a visual comparison will be made to assess the degree of uptake within abnormal tissue [7]. These criteria will have a high probability of distinguishing true complete responders from partial responders. Contrast enhanced CTs will be evaluated via the standard response criteria (Appendix 4).

All PET-CT scans will be centrally reviewed at University College London Hospital. The results from the report will be used to determine the number of further treatment cycle's patients will require, following cycle 1. Copies of locally reported scans (where relevant) should be sent to the central reviewer via the secure NHS Image Exchange Portal system (IEP) for review by the central reviewer (please refer to appendix 7). Sending images via IEP will not apply to sites where patients are scanned at UCLH, however, sites must ensure that the proforma is completed and sent to remind the central reviewer. In addition to sending images via the secure IEP system, sites must email a copy of the Proforma Request form (see Appendix 5 and 6) that is appropriate to each site) to the central reviewer to indicate that an image has been sent via IEP.

The central reviewer will review the image and return the generated report within the appropriate timelines as stated in the table below (see Appendix 7);

All scans for central review to be sent to;

[name]

Consultant in Nuclear Medicine

Institute of Nuclear Medicine, T5

University College Hospital

[name],

[name]

[contact]

Proforma Request form to be emailed to: [[contact]](mailto:[contact]) and  
[[contact]](mailto:[contact])

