## **5.5 *Follow up***

- Patients will be followed up as part of the study for 2 years following completion of treatment.
- Outpatient follow up visits will be carried out **2 monthly** in the first year and **4 monthly** in the second year. Patients will then be followed at the PI's discretion and/or standard care.
- Details of disease progression must be documented on the CRF.
- Any further therapy for metastatic seminoma must be documented on the CRF.

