### **Source Data Verification**

100 % SDV will be performed on informed consent.

100 % SDV will be performed on inclusion / exclusion criteria.

The following data points will undergo SDV for all patients

- Adverse events and toxicities levels;
- Metabolic response rate by FDG PET-CT scan and number of cycles required;
- Follow Up survival dates and progression disease dates for Progression Free Survival and Overall Survival.

100% SDV on all data points will be performed for a minimum of one patient per site or approximately 5% of all patients, whichever is greater.

Reasons for not performing on-site monitoring must be agreed with the CECM Management Team and the Sponsor and be fully documented in the TMF.

Original CRFs will be sent by post from site to the trial coordinator/monitor in a timely manner. Upon receipt of CRFs the trial coordinator/monitor will review for any obvious errors and data queries will be raised.

The following central facilities are utilised in this study:-

- Orchid tissue bank: Queen Mary University of London, Molecular Oncology Unit, [name].
- Central review of scans: University College London Hospital.

The following facility will undergo yearly monitoring visits for the duration of their participation in the study during the recruitment and treatment phase – once the follow-up phase is entered, its involvement with the trial will end. As such, monitoring will cease and the facility will be subject to a close-out visit:

- Orchid tissue bank.

The following facility will undergo 6 monthly monitoring visits for the duration of their participation in the study during the recruitment and treatment phase – once the follow-up phase is entered, its involvement with the trial will end. As such, monitoring will cease and the facility will be subject to a close-out visit:

- University College London Hospital - Institute of Nuclear Medicine

A summary of all monitoring activity for this study will be provided to the Sponsor at least every 6 months.

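### The SAP counts progression only on central imaging review, so a relapse documented at site and then salvaged need not be a PFS event, and it does not say how that patient enters the 39/45 rule

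*SAP*

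**What the plan says.** SAP 3.4.1.1.1 runs PFS from enrolment to "first evidence of disease progression based on central review or death, whichever occurs first". Without an event, "PFS will be censored on the last date the patient was known to be progression-free". On dating it adds: "The PFS time will always be derived based on scan/assessment dates not visit dates". There is no rule for a relapse diagnosed at site, for disagreement between site and central review, or for the start of new anticancer therapy. SAP 7.2.1 calls the trial positive if at least 39 of the first 45 patients are progression-free at 2 years. Protocol 11.5 has the same rule but does not tie progression to central review.

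Central review is described in imaging terms. Protocol Appendix 8 says "Image data must be transferred to UCLH Central Review" and lists PET and CT files. Protocol 5.3.3 adds an emailed request form.

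The protocol collects site information separately. Section 5.5 requires progression details on the CRF and adds: "Any further therapy for metastatic seminoma must be documented on the CRF". The source data verification list in section 10.2 covers, for all patients, "Follow Up survival dates and progression disease dates for Progression Free Survival and Overall Survival".

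**The concern.** The event definition is narrower than the ways in which the trial can detect relapse. Follow-up visits are 2-monthly in year 1 and 4-monthly in year 2, which makes 6 + 3 = 9 visits with examination and tumour markers (Protocol 5.4 and 5.5). A complete metabolic responder has scheduled CTs only at 1 and 2 years post therapy (Protocol 5.3.2). A relapse could therefore come to light between scans and be treated without a centrally read progression.

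Death will not reliably pick up such patients. Of the earlier AUC-10 experience, Protocol 1.3 says: "The relapsed patients were successfully salvaged using conventional chemotherapy". A salvaged patient may be alive with a clear 2-year CT.

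The primary test turns on one patient in 45, so losing even one failure matters.

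**Working it through.** **1. Is the follow-up window covered by central review?**
- The table in Protocol 5.3.3 lists follow-up contrast-enhanced CTs for central report within 2 months.
- Protocol 10.2 says the central imaging facility's involvement ends when the follow-up phase is entered.
- SAP 3.4.1.1.1 needs central review for every progression, and most of the 2-year window lies in follow-up.

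These three cannot all stand.

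**2. What happens to a site-documented, salvaged relapse with no centrally read progression?** It is not an event. Two outcomes fit the text:
- (a) Later CTs up to 2 years are clear and the patient is treated as progression-free.
- (b) He is censored at the last date he was known to be progression-free. The relapse itself causes the censoring, so the censoring is informative, and the SAP does not say how he enters the 39/45 count.

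**3. The plan's own design.** Inputs from SAP section 4 and 7.2.1: n = 45, cut-off 39, p0 = 0.75, p1 = 0.90, one-sided 5%, 80% power, 10% drop-out. With P(X ≥ c | p) = Σ C(45,x) p^x (1−p)^(45−x), summed over x = c to 45:
- P(X ≥ 39 | 0.75) = 0.0446
- P(X ≥ 39 | 0.90) = 0.8415
- 45 is the smallest n that meets both limits, and 45/0.90 = 50

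The stated design reproduces.

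**4. Outcome (a), a fixed number k of hidden failures counted as successes.** The rule passes when 39 − k patients are truly progression-free. At a true rate of 75%:

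| k | True count that passes | Type I error |
|---|---|---|
| 0 | 39 | 0.0446 |
| 1 | 38 | 0.0941 |
| 2 | 37 | 0.1725 |

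Each such patient adds 1/45 = 2.2 percentage points to the observed rate.

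**5. Outcome (a), a share m of failures hidden.** The documents give no value for m, so 5% to 20% is an assumption. Counted rate = 0.75 + 0.25m; expected hidden failures = 45 × 0.25 × m.

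| m | Counted rate | Expected hidden | Type I error |
|---|---|---|---|
| 5% | 0.7625 | 0.56 | 0.0651 |
| 10% | 0.775 | 1.13 | 0.0929 |
| 20% | 0.80 | 2.25 | 0.1768 |

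**6. Outcome (b).** Steps 4 and 5 do not apply, but the Kaplan-Meier estimate still moves. Take 45 patients with 7 true failures: 38/45 = 84.4%. Censor one failure instead of counting it, with no other censoring before 2 years. If he is censored before the other six events, the estimate is 38/44 = 86.4%; if after them, 39/45 = 86.7%. The failure is lost here too, and the 39/45 rule cannot be applied to him as written.

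**The case against.** Central review is a legitimate safeguard in an open-label single-arm trial, and verifying CRF progression dates is compatible with central adjudication. A relapse that is scanned, sent and read centrally as progression is captured, and Protocol 5.3.2 allows CT when clinically indicated. A marker or clinical trigger may well lead to such a scan, and nothing in the documents shows that missed relapses would be common. All of that stands and limits how many patients are affected.

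A reader might also infer more than the text supports:
- *Every such patient is scored progression-free.* The SAP does not say so. A patient with a recorded relapse is not known to be progression-free afterwards, so censoring is at least as natural a reading. For the same reason it cannot be said that the error always adds a success to the count.
- *The central reviewer sees images and nothing else.* A request form is also sent, and its content could not be checked. No available text sends the reviewer markers, biopsy results or clinical findings.
- *The protocol clearly intends every marker or clinical relapse to be a PFS failure.* It has no progression definition specific to PFS. Appendix 2 rests on imaging. Appendix 3 uses marker reduction or progression within 28 days of stopping chemotherapy. SAP 7.3.2 requires new sites of disease, with rising markers if present.

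The reference to assessment dates leaves some room for non-scan evidence when dating PFS, but it does not widen the event definition. None of these points supplies the missing rule.

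**Conclusion.** The concern holds in this form: as written, a site-documented and salvaged relapse without a centrally read progression is not a PFS event. The patient is either scored progression-free or informatively censored with undefined status in the 39/45 count. Either way a failure is lost from the primary analysis, although the trial collects the information needed to count it.

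The size is illustrative. If such patients are counted as successes, type I error at a true 75% rate goes from 4.5% to 9.4% with one hidden failure and 17.3% with two, against the stated 5%. For an assumed 5%, 10% or 20% of failures missed it is 6.5%, 9.3% or 17.7%. The one- and two-patient figures assume exactly that number hidden in every trial. None of these figures applies if the patients are censored. The design figures themselves are correct.

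**What to change.** - In SAP 3.4.1.1.1, define the PFS event as the earliest of centrally read progression, site-documented progression or relapse recorded on the CRF (marker, biopsy, clinical or local imaging), or death.
- State that a patient who starts further therapy for documented relapsed or progressive seminoma counts as a failure in the 39/45 rule. New therapy without documented relapse or progression should not be an event by default.
- Say how patients taken off study for no response (Protocol 3.1) are classified in the primary analysis.
- Keep central-review-only PFS as a sensitivity analysis, so that the effect of site judgement is visible.
- Reconcile Protocol 5.3.3, Protocol 10.2 and SAP 3.4.1.1.1 on whether follow-up scans are centrally reviewed.

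The cost is mainly SAP wording, plus a protocol clarification on central review. Progression and further therapy are already on the CRF. Progression dates are on the list for source verification in all patients; further therapy is not, so it may need adding. The downside is that some events will rest on site judgement, and 2-year PFS may be slightly lower.
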